Standard Operating Procedure

Study Summary

Title	A Randomized Study Evaluating Patients Discharged with Indwelling Chest Tube and Valve				
Running Title	Discharged with Indwelling Chest Tube and Valve				
Protocol Number	17-007774				
Phase	Phase II				
Methodology	Randomized				
Overall Study Duration	5 years				
Subject Participation Duration	30 Days				
Single or Multi-Site	Multi-Site				
Objectives	To assess the efficacy of antibiotics and closer monitoring on decreasing empyema in patients discharging with a chest tube and valve in place as measured by documented empyema following discharge.				
Number of Subjects	560				
Diagnosis and Main Inclusion Criteria	Discharge from the hospital with an indwelling chest tube and valve in place.				
Study Treatment	Oral antibiotics and close monitoring.				
Reference Treatment	Standard of Care				
Statistical Methodology	Comparison of the rate of empyema and readmission in the two arms of the study.				

1 Introduction

This document is a protocol for a human research study. This study will be carried out in accordance with the applicable United States government regulations and Mayo Clinic research policies and procedures.

1.1 Background

Prolonged air leak remains a troublesome problem in general thoracic surgery. Many studies have attempted to identify risk factors for prolonged air leak, which include reduced pulmonary function, use of steroids, upper lobectomy, age, decreased body mass index, and the presence of adhesions, however no one factor is highly predictive for air leak or time to leak closure (1-3). Many adjuncts are used intraoperatively to prevent air leaks, but no consistently effective solution has been discovered (4-5). In the era prior to wide adoption of video-assisted thoracic surgery (VATS), patients underwent thoracotomy and remained in the hospital for multiple days until chest tube removal. During this convalescence, many air leaks would seal. However, in the current era characterized by decreased length of stay, avoidance of hospital acquired conditions, minimally invasive thoracic surgery, and enhanced recovery protocols leading to faster return to activities of daily living, the problem of prolonged air leak is more difficult to manage because patients are not necessarily remaining hospitalized. Further, with quality measurements and economic impacts for early discharge, a prolonged air leak is a much more significant issue, since it significantly increases postoperative length of stay and cost (6-9). Many centers have reported managing this issue with dismissal from the hospital with a chest tube in place connected to a one-way valve mechanism (10-13). However, evidence suggests that the risk of empyema increases with prolonged chest tube duration (14-15).

1.2 Clinical Data to Date

Several studies report prolonged air leak rates in the 10-15% range following lobectomy (1-3). Prolonged air leak has been shown to be a primary driver in prolonged length of stay and increased hospital costs (6-9). Varela and colleagues found air leaks longer than 5 days increased rate of pulmonary complications including atelectasis, pneumonia, or empyema (7). Brunelli and colleagues reported an increased rate of empyema of 8.2% to 10.4% in patients with prolonged air leaks lasting more than 7 days versus only 0% to 1.1% in patients with shorter air leaks (14). This study also showed that longer air leaks led to further interventions; however, this was not in patients discharged from the hospital (14).

Dismissal from the hospital with a chest tube in place is not a novel concept. Multiple groups have advocated for this practice. McKenna and colleagues reported on fast-tracking thoracoscopic patients. They utilized this strategy in 2.5% of patients (7/282) and reported only one patient required readmission (12). Another study by Rieger et al. utilized the mini-Atrium[®] device for dismissal of patients with a chest tube in place for either effusions or air leak. They reported a rate of minor complications in 11% (4/36), which included 3 readmissions, one of which was for an empyema (13). Royer et al. described similar practice with dismissal of 65 patients with a chest tube and Heimlich

valve (13%, 65/496). Two patients were readmitted and 4 had superficial site infections requiring oral antibiotics but no empyema was reported. Overall they reported a potential savings of 305 inpatient hospital days (11). In light of these findings, hospital length of stay is decreased and, concurrently, cost with this practice. These studies encourage the practice with little complications.

Reinersman and colleagues evaluated outcomes of patients discharging with an indwelling chest tube from a high volume referral center. At the institution all patients who are discharged with an indwelling chest tube receive standard education from our nursing staff as to dressing changes, changing the dressing when saturated, and noting daily output and changes in output. All patients are instructed on how to check the device for air leak. If they notice the leak has ceased, they are to call for the next available appointment to be seen in clinic for possible chest tube removal. Additionally, all patients receive a standard dismissal education pamphlet summarizing the care of the chest tube and Heimlich valve or mini-Atrium[®]. They found that the rate of empyema was 16.5%, using strict criteria, including all patients with a leukocytosis or fever and an undrained effusion on chest x-ray or CT scan. The rate of readmission with a chest tube in place was found to be 25%.

Reinersman and colleagues found male gender, a history of coronary artery disease and peripheral vascular disease were found to be predictors of empyema (15). Traditional predictors of air leak were analyzed including pleural adhesions, chronic obstructive pulmonary disease, upper, age, use of steroids and decreased body mass index (1-3). These traditional predictors did not contribute to risk of empyema and readmission in their study. The number of patients who were on immunosuppressive medications was too small to determine a difference. The presence of diabetes approached significance but was not a major predictor. Examining reoperative surgery as a surrogate for pleural adhesions also did not show a statistically significant difference in rate of empyema or readmission (p=0.2) (15).

As previously discussed, Brunelli et al. reported that the presence of an air leak greater than 7 days led to a higher rate of empyema compared to patients without air leak or with a shorter duration air leak (14). Reinersman et al. also revealed a temporal relation to number of days with air leak and chest tube related to risk of empyema. The overall number of days with chest tube in place was found to be a predictor of empyema, with an incremental increase per one day with chest tube (HR 1.2, p=0.006). Further, the presence of an air leak and chest tube for more than 14 days markedly increased the risk of empyema (HR 7.6, p=0.047) (15).

1.3 Risks and Benefits

All study interventions could be considered standard of care.

Cerfolio and colleagues cite the use of oral antibiotics while the chest drain is in place but they do not address any risks or benefits but state it is merely their preference (3). In the study conducted by Reinersman and colleagues, the 27 patients discharging with indwelling chest tubes in place that received prophylactic antibiotics at discharge were found to have no complications from the antibiotics (15). Cerfolio, Reinersman and colleagues have reported that an air leak lasting longer than 7 days leads to an increased risk of empyema (14, 15).

The Surgical Care Improvement Project (SCIP) Performance Measures endorse pprophylactic antibiotics discontinued within 24 hours after surgery end-time. There is no significant evidence showing a benefit to continuing antibiotic usage beyond 24 hours. Prolonged administration of antibiotic usage may increase the risk of drug resistance and secondary infections, such as *Clostridium difficile* (16).

2 Study Objectives

Primary Objective

To assess the efficacy of antibiotics and closer monitoring on decreasing empyema in patients discharging with a chest tube and valve in place as measured by documented empyema following discharge.

Secondary Objective

To assess the efficacy of antibiotics and closer monitoring on decreasing hospital readmissions while the chest tube and valve are in place as measured by readmission to the hospital following hospital discharge after the initial surgical intervention.

3 Study Design

3.1 General Description

This study is a multicenter, randomized trial for the treatment of subjects discharging from the hospital with a chest tube and valve in place. Subjects will be screened prior to discharging from the hospital and interested qualified subjects will be consented and offered participation in this trial. Once consent has been obtained the subject will be randomized to receive oral antibiotics and close monitoring, defined as twice weekly telephone calls by a member of the care team, of their chest tube and valve or standard of care, defined as no calls from the care team but waiting for the subject to contact the care team when the air leak has stopped. The subject will be followed until they have their chest tube removed.

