3.3 Duration of Participation

Subjects will participate in the study for 30 days following discharge from the hospital or until the chest tube has been removed if it remains in place more than 30 days post hospital discharge.

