4.1 Inclusion Criteria

- ≥ 18 years of age
- Male or Female
- Consultation with a thoracic surgeon
- Discharge from the hospital with a chest tube and valve in place
- Subject is able to understand the study procedures and provide informed consent.

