4.3 Subject Recruitment, Enrollment and Screening

A member of the research team will identify that a potential subject is going to be discharged from the hospital with a chest tube and valve in place. Once the subject's eligibility for the study has been determined the background of the proposed study and the benefits and risks of the study and procedures will be explained to the subject as a part of consenting process.

A signed, written informed consent document will be obtained from each subject by the investigator or his/her designee prior to the subject's involvement in the study. Routine clinical evaluations that would be performed as part of the normal clinical care of patients may be performed prior to such consent and used as part of the screening assessment. If the patient is subsequently consented and enrolled in the study, the results of such tests may be used as study data.

The process of obtaining informed consent will include the investigator or investigator's designee informing all subjects about:

- The expected duration and purpose of the study.
- The method of application and investigational nature of the device.

- The potential risks and benefits that may result from utilization of the device.
- The right to refuse participation in this clinical investigation and that if they should choose to participate, they may withdraw from the study at any time.

After consenting, subjects will be considered enrolled if they meet all the inclusion criteria and none of the exclusion criteria. Subjects who fail to meet any of the entry criteria will be excluded from the study and considered a screen failure. Screen failures will be recorded, and the reason(s) for exclusion will be documented.

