4.4.2 Data Collection and Follow-up for Withdrawn Subjects

Information collected before the participant withdraws consent can continue to be used; however, new information will not be collected.

5 Study Procedures

5.1 Visit 1

The subject will be identified for eligibility into the study. The study coordinator will consent and enroll the subject. For women of childbearing potential, a pregnancy test will be done if not done prior to surgery and it must be negative before you can continue in this study. Baseline data collected will include air leak status and surgical history.

5.2 Visit 2

Prior to their discharge from the hospital a member of the study team will review the instructions for completing the Patient Chest Tube Diary and will confirm that the standard clinical education for discharging with an indwelling chest tube and valve has been completed. For subjects randomized to Group 1 confirm that they have received their prescription for antibiotics. The antibiotic to be prescribed is cephalexin; it is the oral equivalent of the antibiotic used for perioperative coverage. In the event that the subject has an allergy to cephalexin or the cephalosporin group of antibiotics then clindamycin should be prescribed instead in following the typical perioperative coverage.

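### Randomisation is tied to consent rather than to confirmed discharge with the tube, although eligibility and the 30-day window both depend on that later discharge

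*Protocol*

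**What the plan says.** On timing, section 3.1 of the protocol says: "Subjects will be screened prior to discharging from the hospital and interested qualified subjects will be consented and offered participation in this trial". It continues: "Once consent has been obtained the subject will be randomized". Section 5.2 places Visit 2 before discharge and makes it arm-specific: "For subjects randomized to Group 1 confirm that they have received their prescription for antibiotics". The arm is therefore known while the patient is still in hospital. No placebo or masking is described, and the arms differ visibly in prescription, telephone calls and diary.

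On eligibility, section 4.1 lists "Discharge from the hospital with a chest tube and valve in place" as an inclusion criterion. Section 4.3 says that the research team first identifies that "a potential subject is going to be discharged from the hospital with a chest tube and valve in place". It then adds: "After consenting, subjects will be considered enrolled if they meet all the inclusion criteria and none of the exclusion criteria". For the rest: "Subjects who fail to meet any of the entry criteria will be excluded from the study and considered a screen failure".

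On follow-up and analysis, section 3.3 says: "Subjects will participate in the study for 30 days following discharge from the hospital", or longer if the tube is still in. Section 6.2 counts empyema over 30 days after discharge and makes intention to treat the primary analysis; section 6.3 repeats this.

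**The concern.** Three events that should coincide are separated. Allocation follows consent, while eligibility and time zero for the outcome both wait for discharge. Two problems can arise in the gap.

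First, a randomised patient may have the tube removed before leaving, or may not leave. Sections 6.2 and 6.3 would keep that patient in the comparison, where the trial's question no longer applies. Section 4.3 could be read as removing the same patient as a screen failure, after staff know the arm. Keeping such patients weakens the contrast; removing them after open allocation gives up the protection of randomisation. An empyema between allocation and discharge also falls before the window as worded.

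Second, staff who know the arm take part in deciding when the patient leaves and when the tube comes out. Section 1.2 reports a hazard ratio for empyema of 1.2 per additional day with the tube, so a difference between arms in the timing of discharge or tube removal could matter to the outcome being compared.

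**Working it through.** **Inputs**
- Two-sided alpha 0.05, power 80%, 50% reduction, 253 per arm, 10% dropout allowance, 560 in total: section 6.1.
- Control rate p1 = 16.5%: an assumption. Section 6.1 states none; this is the background rate in section 1.2 for patients sent home with a tube. Then p2 = 8.25%.
- Empyema rate b in patients randomised but not exposed: assumed 0% to 1.1%, the section 1.2 figure for shorter air leaks.
- Share f of such patients: not in the protocol; 5%, 10% and 15% are illustrations.

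**Reproducing the plan's figure**

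n per arm = [1.960 × √(2p̄(1−p̄)) + 0.842 × √(p1(1−p1) + p2(1−p2))]² / (p1−p2)², where p̄ is the mean of p1 and p2.

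With p̄ = 0.12375 this is (0.9127 + 0.3889)² / 0.0825² = 1.694 / 0.006806 = 248.9, so 249 per arm. The plan has 253, a difference of 1.6%, so 16.5% is a reasonable reading of the planning rate. For dropout, 506 / 0.9 gives 563 and 506 × 1.1 gives 557; the stated 560 lies between them.

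**Dilution**

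Each arm's rate becomes (1−f) × rate + f × b, and the difference shrinks to (1−f) × 8.25 points.

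Power = Φ{[(p1−p2)√n − 1.960 × √(2p̄(1−p̄))] / √(p1(1−p1) + p2(1−p2))}.

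Example with f = 10%, b = 0, n = 253: the rates are 14.85% and 7.425%, and Φ[(1.1810 − 0.8720) / 0.4418] = Φ(0.699) = 75.8%.

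| Share f | Rates at b = 0 | Rates at b = 1.1% | Power, 253 per arm | Power, 280 per arm | n per arm for 80% |
|---|---|---|---|---|---|
| 0% | 16.5% v 8.25% | same | 80.6% | 84.4% | 249 |
| 5% | 15.68% v 7.84% | 15.73% v 7.89% | 78.1-78.3% | 82.1-82.3% | 264-266 |
| 10% | 14.85% v 7.43% | 14.96% v 7.54% | 75.4-75.8% | 79.6-79.9% | 281-284 |
| 15% | 14.03% v 7.01% | 14.19% v 7.18% | 72.5-73.1% | 76.8-77.3% | 300-304 |

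The 280 column assumes that everyone enrolled is analysed. If ordinary dropout uses the whole allowance, 280 × 0.9 = 252 remain and the 253 column applies. At f = 1% to 2% the loss is negligible: 80.2% to 79.7% at 253 per arm.

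**Sensitivity to b**

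If non-exposed patients instead carried the control risk of 16.5% in both arms, power at f = 5%, 10% and 15% would be 75.9%, 70.7% and 65.1% at 253 per arm, and 80.0%, 75.0% and 69.5% at 280.

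**Excluding instead of keeping**

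If such patients were dropped, n would become (1−f) × n at the undiluted rates. Power would be 78.6%, 76.4% and 74.0% from 253, and 82.6%, 80.5% and 78.2% from 280. At b of 0% to 1.1%, exclusion therefore recovers at most about 1.5 points of power, and it does so by selecting after open allocation.

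The effect of arm knowledge on discharge timing cannot be sized from the protocol.

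**The case against.** The strongest reply is that section 3.1 fixes an order, not an interval. A reader might infer that patients are allocated immediately after consent, at Visit 1. The text does not say so: section 5.1 mentions consent and enrolment but not randomisation, and the schedule of events has no randomisation row. Allocation on the day of discharge is already compatible with the wording. Some allocation before the patient leaves is also unavoidable, because the Group 1 prescription is confirmed at Visit 2.

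Section 4.3 is a real safeguard as well. Candidates are patients already identified as going home with a tube, and eligibility is assessed before the consent discussion. The share later found not to qualify could be close to zero. The 0% to 1.1% rate is borrowed from a study that section 1.2 says was not in discharged patients. No passage suggests that a prescription, calls after discharge or a diary item changes the date of discharge. The rule for counting such patients could also sit in a statistical analysis plan.

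Most of this stands, and it limits the size of the point. It does not remove it. Wording that permits allocation at discharge equally permits it days earlier, and the moment of allocation is a protocol matter. Nor does section 4.3 say whether a screen failure can be declared after randomisation, which leaves it in tension with the intention-to-treat rule.

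**Conclusion.** The point holds as a conditional one. The protocol lets open allocation precede the event that defines both eligibility and time zero, and it leaves unsettled whether a randomised patient who does not go home with the tube is kept or excluded. Avoiding this is cheap.

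The size is probably modest. Under the assumed 16.5% control rate, a halved rate in the other arm, and 0% to 1.1% empyema in non-exposed patients, shares of 5%, 10% and 15% give about 78%, 75-76% and 73% power at 253 per arm, and about 82%, 80% and 77% at 280. The planned 80% is roughly kept up to a 10% share, provided that ordinary dropout does not also use the allowance.

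A reader might go further and conclude that the primary comparison is diluted, or that discharge timing is biased by arm. The protocol supports neither as fact. It gives no share of non-exposed patients and no evidence that discharge depends on the arm; it only leaves both routes open.

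**What to change.** Amend sections 3.1 and 5.2 as follows:
- Consent is taken at Visit 1.
- Randomisation in the Balance module takes place at Visit 2 on the day of discharge, after the decision to discharge is final and tube and valve are confirmed in place, and before the Group 1 prescription is confirmed.
- Patients whose tube is removed before that step are screen failures under section 4.3.
- Every patient who is randomised stays in the intention-to-treat set.

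Allocation, confirmed eligibility and the start of the 30-day window then fall on essentially the same day.

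The cost is a few sentences and a later step in a randomisation system already planned. The downside is that staff must be available to randomise on the day of discharge, and a few consented patients will never be randomised.

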3.5 Secondary Study Endpoints

Reduction of 30-day readmission in patient's discharging with an indwelling chest tube and valve.

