5.5 Off Study

Subjects will be followed for 30 days following discharge from the hospital or until the chest tube has been removed if it remains in place for more than 30 days post hospital discharge. The patient will be instructed to return their Patient Chest Tube Diary at their next visit or via mail if they did not use the electronic app. A telephone call may be made in order to remind the participants to return their daily diary. Attachment 14.3.

Schedule of Events						
Study Activity	Visit 1	Visit 2	Daily Diary	Twice Weekly Calls ^a	Off Study	
Informed Consent	х					
Air Leak Status	Х					
Surgical History	Х					
Patient Education		х				
Patient Chest Tube Diary			x			
Telephone Assessment				Х		
Adverse Event Evaluation			Х	Х	х	
a: Group 1 only. b: Includes microbiology assessment of infection if done as part of clinical care and data is available.						

6 Statistical Plan

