6.2 Statistical Methods

Descriptive Statistics

Descriptive statistics for baseline and clinical variables will be reported as number (percentage) for discrete variables and as mean (SD) or median (range) as appropriate for continuous variables. Baseline demographic and clinical variables will be reported by treatment group. These assessments will help identify potential confounding variables to be used as covariates in multiple variable models when examining the outcomes between treatment arms.

Handling of Missing Data

In the event that we have patients without complete follow-up survival analyses for the outcomes of 30 day empyema and 30 day readmission will be utilized to account for differential patient censoring.

Multiplicity

This study has two treatment arms being compared. No multiple comparison adjustments are planned.

Primary Hypothesis: Assess whether patients receiving antibiotics and twice weekly calls have reduced 30-day **empyema** rates post-discharge compared to patients on standard of care.

The primary analysis will be intention to treat (ITT). The proportion of patients having 30-day empyema in the two treatment arms will be estimated and reported along with a 95% confidence interval. The association of treatment arm with the rate will be assessed using a Chi square test. Additionally, logistic regression will be used to examine the treatment effect accounting for baseline covariates in which there is important imbalance between treatment arms. If not all patients having complete follow-up to 30 days post-discharge then these same analyses will be performed using survival methods, estimates of survival-free of empyema using Kaplan Meier methods and Cox models for the assessment of the association of treatment arm and the risk of empyema. The alpha level will be set at 0.05 for statistical significance.

Secondary Hypothesis 1: Assess whether patients receiving antibiotics and twice weekly calls have reduced 30-day **readmission** rates post-discharge compared to patients on standard of care.

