For this study, the study treatment follow-up period is defined as the time of consent until 30 days following hospital discharge or until the removal of the chest tube if after 30 days.

Preexisting Condition

A preexisting condition is one that is present at the start of the study. A preexisting condition should be recorded as an adverse event if the frequency, intensity, or the character of the condition worsens during the study period.

General Physical Examination Findings

At screening, any clinically significant abnormality should be recorded as a preexisting condition. At the end of the study, any new clinically significant findings/abnormalities that meet the definition of an adverse event must also be recorded and documented as an adverse event.

Post-study Adverse Event

All unresolved adverse events should be followed by the sponsor-investigator until the events are resolved, the subject is lost to follow-up, or the adverse event is otherwise explained. At the last scheduled visit, the sponsor-investigator should instruct each subject to report, to the sponsor-investigator, any subsequent event(s) that the subject, or the subject's personal physician, believes might reasonably be related to participation in this study.

Abnormal Laboratory Values

A clinical laboratory abnormality should be documented as an adverse event if it requires active management or treatment.

Hospitalization, Prolonged Hospitalization or Surgery

Any adverse event that results in hospitalization or prolonged hospitalization should be documented and reported as a serious adverse event unless specifically instructed otherwise in this protocol. Any condition responsible for surgery should be documented as an adverse event if the condition meets the criteria for an adverse event.

Neither the condition, hospitalization, prolonged hospitalization, nor surgery are reported as an adverse event in the following circumstances:

 Hospitalization or prolonged hospitalization for diagnostic or elective surgical procedures for a preexisting condition. Surgery should **not** be reported as an outcome of an adverse event if the purpose of the surgery was elective or diagnostic and the outcome was uneventful.

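### Section 3.1 ends follow-up at chest tube removal, contradicting the 30-day follow-up and 30-day analyses elsewhere; the readmission objective and the empyema endpoint leave the window just as unclear

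*Protocol*

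**What the plan says.** The protocol gives two different ends of follow-up.

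- 3.1 General Description: "The subject will be followed until they have their chest tube removed". No minimum number of days is attached.
- Section 3.3, on how long patients take part, reads: "Subjects will participate in the study for 30 days following discharge from the hospital or until the chest tube has been removed", the second limb applying only to a tube still in beyond day 30. Section 5.5 Off Study repeats this: "Subjects will be followed for 30 days following discharge from the hospital or until the chest tube has been removed", with the same condition. The adverse event reporting period in 7.1 is "the time of consent until 30 days following hospital discharge or until the removal of the chest tube if after 30 days".

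The outcome windows also differ.

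- Readmission: the secondary objective in section 2 speaks of "decreasing hospital readmissions while the chest tube and valve are in place", then adds a measurement clause (readmission after discharge from the index surgery) without a tube limit. Section 3.5 has "Reduction of 30-day readmission in patient's discharging with an indwelling chest tube and valve", and 6.2 analyses the 30-day proportion.
- Empyema: the primary objective is "as measured by documented empyema following discharge", with neither a tube limit nor a day limit. Section 3.4 gives no window. The 30 days appears only in 6.2: "The proportion of patients having 30-day empyema in the two treatment arms will be estimated".

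**The concern.** For any patient whose tube comes out before day 30, 3.1 and 3.3 cannot both be followed. This matters more than an ordinary wording slip because tube removal happens after randomization and may depend on the arm. Under 3.1 and 5.4, Group 1 is telephoned twice a week and asked about the leak, while the control arm waits for the patient to report that it has stopped. Earlier removal in Group 1 is therefore plausible, although the protocol neither claims it nor gives a size.

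If observation stopped at removal, empyema or readmission between removal and day 30 would go unrecorded, and the arm with earlier removal would have less time in which to register an event. In a multisite trial, some sites could work to one rule and some to the other, and events not collected at the time may not be recoverable.

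**Working it through.** **1. The texts side by side.** Take a patient whose tube is removed on day 12 and who develops empyema on day 20.

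- Under 3.1, follow-up ended on day 12 and the event is not observed.
- Under 3.3, 5.5 and 7.1, follow-up runs to day 30 and the event is observed.
- Under 6.2, it counts as a 30-day empyema. Section 3.4 does not say.
- If the event is a readmission, 3.5 and 6.2 count it. The opening of the secondary objective does not; its measurement clause could.

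**2. The plan's own figure.** Section 6.1 states 253 per arm for a 50% reduction in empyema (two-sided 0.05, 80% power) but gives no control rate. Assume the 16.5% quoted in 1.2, so p1 = 0.165, p2 = 0.0825 and mean 0.12375:

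n = [1.960 × √(2 × 0.12375 × 0.87625) + 0.842 × √(0.165 × 0.835 + 0.0825 × 0.9175)]² / 0.0825² = (0.913 + 0.389)² / 0.00681 ≈ 249 per arm.

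This agrees with 253 to within 3%. For dropout, 506 × 1.1 = 557 and 506 / 0.9 = 563, on either side of the stated 560. The calculation does not use the disputed window, so correcting the window leaves the sample size alone.

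**3. Illustration if 3.1 were followed everywhere.** None of these assumptions is in the protocol: 16.5% is a 30-day risk, the hazard is constant and unrelated to the tube, treatment has no effect, every tube in an arm comes out on one fixed day, all sites use 3.1, and all 280 per arm are evaluable.

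- Daily hazard: −ln(1 − 0.165) / 30 = 0.00601.
- Observed risk with removal on day d: 1 − exp(−0.00601 × d).
- False-positive rate: probability that the uncorrected chi-square test is significant, summed over two independent binomials with 280 each.

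| Removal day, Group 1 vs control | Observed empyema | Ratio | False-positive rate |
|---|---|---|---|
| 14 vs 14 | 8.1% vs 8.1% | 1.00 | 5% |
| 13 vs 14 | 7.5% vs 8.1% | 0.93 | about 6% |
| 12 vs 14 | 7.0% vs 8.1% | 0.86 | 8% |
| 10 vs 14 | 5.8% vs 8.1% | 0.72 | 18% |

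With 253 per arm, the last row gives about 17%. With every patient followed to day 30, the ratio is 1.00 whatever the removal days.

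**4. If risk falls after removal.** Let the hazard halve once the tube is out, keeping the control 30-day risk at 16.5% with removal on day 14. The tube-in hazard is then 0.1803 / (14 + 0.5 × 16) = 0.00820. For 10 versus 14 days:

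- Tube-limited window: 7.9% vs 10.8%, ratio 0.73.
- 30-day window: 1 − exp(−0.00820 × 20) = 15.1% vs 16.5%, ratio 0.92.

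Part of the apparent benefit is now real, and the distortion is the gap between 0.73 and 0.92. If no risk remains after removal, the two windows agree and there is no distortion.

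**5. Would the survival fallback repair it?** Section 6.2 turns to Kaplan-Meier and Cox methods when follow-up is incomplete. These require censoring to be unrelated to later risk. Removal follows leak closure, and 1.2 reports empyema risk rising with tube days (hazard ratio 1.2 per day) and with leak and tube beyond 14 days (7.6). Censoring at removal may therefore be informative, and these methods would not reliably correct it. Nor do they settle which readmissions count.

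No readmission figure is given here, because the 25% in 1.2 is a rate with the tube in place and not a 30-day risk.

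**The case against.** The strongest reply is that the operative text is already right. Sections 3.3, 5.5 and 7.1 agree on at least 30 days, 3.5 and both analyses in 6.2 use 30 days, and the primary objective has no tube limit. The sentence in 3.1 is an outlier in an overview, and no planned analysis uses a tube-limited window. This stands. A reader might infer that both planned comparisons are biased; the documents do not support that, because the bias arises only if sites work to 3.1 or the objective is applied literally.

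A reader might also infer that the secondary objective defines a tube-only endpoint. Read in full, the sentence is ambiguous rather than tube-limited.

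The reply is also right about the numbers. The tube durations are invented, and small differences barely move the error rate. A constant hazard sits poorly with the tube-duration hazard ratios in 1.2. If risk is concentrated while the tube is in, few events follow removal, and earlier removal is a genuine benefit of the monitoring under test. So 18% is not an expected error rate, and the protocol does not show that a large share of events would be lost.

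What the reply does not remove is the contradiction. The participant materials do not settle it either: the Group 2 diary ends with the removal date (14.1), and the diary-return script asks only about removal and the diary (14.3). A site could reasonably take removal as the end of follow-up.

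**Conclusion.** Wrong as written: the protocol contradicts itself on when follow-up ends and on which readmissions count, and leaves the empyema window out of 3.4. Severity is moderate. This is an inconsistency that could truncate endpoint collection at an event the intervention may influence, not a demonstrated bias in the planned analysis. If 3.3 and 5.5 govern, the 30-day comparisons are unaffected.

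The size of the conditional effect cannot be determined from the protocol. The illustrative range of about 6% to 18% for empyema depends on all the assumptions in step 3. It would be diluted if only some sites followed 3.1, and the distortion would shrink, possibly to nothing, if risk falls after removal.

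**What to change.** - **3.1:** replace the last sentence so that it matches 3.3 and 5.5. All patients are followed for endpoints through day 30 after discharge, whether or not the tube is out, and longer if it remains.
- **Section 2, secondary objective:** reword to any hospital readmission within 30 days of discharge.
- **3.4:** state the 30-day window for empyema.
- **3.4 and 3.5:** state that events after tube removal through day 30 count.

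The cost is a few sentences in an amendment and a note to sites. The follow-up is already planned in 3.3 and 5.5, and the sample size and analysis methods stay as they are.
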